**1. Abstract**

Many questions related to human somatic sensation and motor control cannot be assessed by research in non-human primates. Our preliminary studies point to the normal and pathologic mechanisms of sensory and motor function. We now propose, in patients undergoing stereotactic surgery for movement disorders and pain, to record the activity of single neurons, multiple neurons (local field potentials - LFP), electrocorticography (ECoG), and EEG.

The first hypothesis of this proposal is that thalamus, ventral striatum (deep structures), and thalamo-cortical ensembles are involved in signaling acute pain, and that abnormal activity in these structures is responsible for many of the symptoms found in neuropathic pain. This activity may also be related to pain-related attention and learning tasks.

The first hypothesis of this proposal will be approached by recording thalamo-cortical activity in response to painful and nonpainful peripheral stimuli, during awake stereotactic procedures for movement disorders and pain. We will also study the effect of attention, cognitive and learning tasks upon the recorded and behavioral response to painful and nonpainful somatic stimuli. The recording data will be analyzed for evidence of activation, evoked potentials, and functional connectivity between different forebrain structures. These results will be interpreted as evidence of networks subserving both pain and psychological processes influencing pain. Significance of the responses to these stimuli will also be assessed by the response to stimulation in the same structures. These studies will provide important direct evidence of the networks and patterns of forebrain activity associated with acute and chronic pain, and will complement the results of animal studies.

Attempts to understand many movement disorders such as Parkinson's disease (PD), dystonia, or essential tremor are limited by the lack of convincing primate models of these conditions. In this proposal, our second hypothesis is that many hyperkinetic disorders are the result of abnormal processes which distort signals between the basal ganglia and the thalamus (deep structures) and the cortex. Interpretation of the results will focus upon networks as revealed by activation and functional connectivity between these forebrain structures. Further evidence of these networks will be assessed by the effects of electrical stimulation carried out during surgery for treatment of movement disorders and pain, including subcortical stimulation, direct motor cortex stimulation with electrical pulses (direct pulsed cortical stimulation), and scalp-applied transcranial direct current stimulation (tDCS).

Recent demonstrations that the mechanisms of action of deep brain stimulation take place partly in motor cortex (Gradinaru V et al., 2009, Payoux P et al., 2004) and the fact that cortical stimulation can modulate neural activity at the basal ganglia level (Strafella AP et al., 2004 , Q Li et

Date: February 19, 2023

Principal Investigator: [name].

Application Number: NA\_00079932

al., 2012), imply that noninvasive brain stimulation and direct pulsed cortical stimulation could be used to demonstrate cortical and subcortical network functional connectivity. Additional uses include the possibility of integrating cortical and subcortical brain stimulation (de Hemptinne et al., 2013). These studies have the potential to clarify the etiology of movement disorders and to map avenues for their treatment.

The speech production system which is disrupted in Parkinson's Disease and other movement disorders, might provide a unique possibility for investigating the neurophysiology of motor control in the human brain. Hypophonia and hypokinetic dysarthria are prevalent in patients with Parkinson's disease (PD). Deep brain stimulation of the subthalamic nucleus does not result in consistent improvement in speech and can negatively impact language function. These observations indicate an important role for the basal ganglia in the speech production system. However, due to the limited knowledge about the role of the basal ganglia in speech production and control, the neurophysiology of the speech related symptoms of the Parkinson's disease are poorly understood and the clinical treatments are very limited. Investigation of the structural organization and function of basal ganglia in the speech motor system will provide significant opportunities for understanding the neurophysiology of the basal ganglia and the pathophysiology of PD and might facilitate the pathway for more efficient treatment of PD symptoms, particularly speech related disorders.

## 2. Objectives

### **Objective I:**

Objective I is to assess the hypotheses that the cortex and deep nuclei of the brain (e.g. thalamus, ventral striatum) are involved in signaling acute pain, and that abnormalities of this region are responsible for many of the symptoms found in neuropathic pain.

The primary outcome is to assess the effect of painful and nonpainful somatic stimuli upon ongoing and evoked spike, local field potential, and EEG activity recorded from cortical and deep nuclei in response to painful stimuli. Non-invasive EEG will be used in healthy subjects and chronic pain patients. Analysis of these results for functional connectivity will allow us to characterize networks subserving pain processing and their disruption or augmentation in chronic pain.

The secondary outcome is to determine the effect of attention, along with cognitive and learning tasks involving somatic stimuli upon ongoing and evoked activity, local field potential and EEG activity recorded from cortical and deep nuclei. Non-invasive EEG will be used in healthy subjects and chronic pain patients. Analysis of these results for functional connectivity will allow us to characterize networks subserving pain related cognitive processes and their disruption or augmentation in chronic pain.

### **Objective II:**

Objective II is to test the hypothesis that actual and imagined movements and movement disorders are the result of ongoing and movement related activity of single neurons, local field potentials and EEG activity recorded from cortical structures and deep nuclei (basal ganglia and thalamus).

Date: February 19, 2023

Principal Investigator: [name].

Application Number: NA\_00079932

The primary outcome is to establish the effect of ongoing and evoked spike, local field potential and EEG activity recorded from cortical and deep nuclei upon movement disorders such as tremor, Parkinson's disease, dystonia and dyskinesia. Analysis of these results for functional connectivity will allow us to characterize networks involved in movement disorders.

Secondary outcomes will include determination of the influence of actual and imagined movements upon ongoing and movement related spike, local field potential, and EEG activity recorded from cortical and deep nuclei.

We also will investigate the effects of direct cortical stimulation with electrical pulses on the motor cortex and other cortices by measuring electrophysiological signals, and will evaluate stimulation effects on disease symptoms.

Additionally, we will determine whether scalp-applied tDCS over the motor cortex also results in modulating single neuron spiking activities or changes in cortical phase –amplitude coupling.. This will be helpful in providing more understanding of the mechanisms of action of DBS and tDCS, and may indicate the usefulness of integrating the two different types of brain stimulation in the future.

Other secondary outcomes will determine whether motor learning or adaptation are the result of ongoing and movement related spike, local field potential and EEG activity recorded from cortical and deep nuclei.

Other secondary outcomes will also include the determination of the mechanisms of speech characteristics as coded in the basal ganglia-thalamocortical network during production and auditory processing of speech based on specific task related spike, local field potential, and EEG activity recorded from cortical and deep nuclei.

### **3. Background**

This application proposes to measure CNS activity in healthy subjects, patients with chronic pain from knee osteoarthritis, patients with chronic pain from chronic widespread pain or fibromyalgia, and in patients undergoing micro- and macro electrode mapping during stereotactic surgery for the treatment of movement disorders or pain. Objective I will involve some form of sensory stimulation (e.g. somatic, visual, auditory, etc.) during recordings (EEG, local field potentials - LFP) from cortex, deep structures such as thalamus, and basal ganglia (ventral striatum, pallidum etc). For example, patients might rate a somatic stimulus while evoked potentials are measured to provide evidence that electrical events in the brain are related to psychophysical ratings of sensation. This result might be interpreted as evidence that the electrode site is involved in processing of somatic sensation.

Objective II will undertake studies of actual movement, imagined movement or movement disorders. During these types of movement recordings will be carried out through the same structures

Date: February 19, 2023

Principal Investigator: [name].

Application Number: NA\_00079932

as described above. Studies of actual and or imagined movement will be carried out by asking patients to carry out imagined movements or actual movements. Disordered movements will be studied by observing spontaneous movements or asking the subject to carry out maneuvers which provoke these movements. These maneuvers will include distraction tasks like mental arithmetic which provokes parkinsonian tremor. We now propose to analyze activation and functional connectivity between deep brain and cortical structures.

Activation by sensory stimuli or movements will be determined by examining changes in neuronal firing rates, ongoing EEG frequency and spectral power as recorded from the structures named above. Cortical or deep structures jointly processing sensory signals will be identified by calculation of correlation, coherence and causality between the EEGs or LFPs recorded from these structures in response to sensory stimuli. Coherence is a measure of synchrony (and functional connections) between signals from different electrodes, and causality is a measure of the extent to which signals at one electrode are causal of those at another electrode (Glaser and Ruchkin, 1976; Granger, 1969; Liu et al., 2011c). All regulatory aspects of this study will be the responsibility of the study coordinator ([name]) and the PI.

Transcranial direct current stimulation (tDCS) is a commonly used non-invasive form of brain stimulation for studying motor functions in health and disease. It involves the attachment of surface electrodes to the scalp through which very small electric currents (1 or 2mA) are applied via a current regulated device that is powered by a battery. The currents do not produce any sensation. Importantly, when the electrode is placed over the region of the motor cortex, the small currents appear to affect the excitability of the neural tissue, as measured by the size of the motor evoked potential (MEP) induced by a single pulse of transcranial magnetic stimulation and recorded in hand muscles. tDCS will be used intraoperatively to demonstrate the functional connectivity between primary motor cortex and the subthalamic nucleus. We wish to characterize the mechanisms of action of tDCS as a noninvasive cortical stimulation for motor symptom control in PD patients (Benninger et al., 2010).

Recently, research into the impact of tDCS in Parkinson's patients has been growing. Early studies indicated motor function improvement as a result of the anodal stimulation of M1 (Fregni et al., 2006). Other investigations into the effects of tDCS on motor symptoms have demonstrated improvements in gait and bradykinesia (Benninger et al., 2010) and improvements in tapping and pointing movements (Grüner et al., 2010). More recent motor symptom studies have shown significant improvements in gait with reductions in freezing-of-gait episodes (Valentino et al., 2014; Von Papen et al., 2014) as well as increases in trunk velocity and average sway (Kaski et al., 2014). Additionally, tDCS prompted prolonged improvements in tests to measure executive function (Doruk et al., 2014) and time up and go task performance (Manenti, R. et al. 2014). tDCS will be used intraoperatively to demonstrate the functional connectivity between primary motor cortex and the subthalamic nucleus. We wish to characterize the mechanisms of action of tDCS as a noninvasive cortical stimulation for motor symptom control in PD patients.

Synchronous, rhythmic changes in the membrane polarization of neurons form oscillations in local field potentials. It is hypothesized that high-frequency brain activity reflects local cortical information processing, and low-frequency brain rhythms project information flow across larger

Date: February 19, 2023

Principal Investigator: [name].

Application Number: NA\_00079932

cortical networks (Zheng and Colgin, 2015). This provides for a complex form of information transmission due to interactions between oscillations at different frequency bands, which can be displayed using cross-frequency coupling (CFC) metrics. Phase-amplitude coupling (PAC) is one of the most common representations of the CFC. PAC reflects the coupling of the phase of oscillations in a specific frequency band to the amplitude of oscillations in another frequency band. In a normal brain, multi-item working memory is accompanied by PAC in the hippocampus, and changes in PAC have been associated with diseases such as schizophrenia (Allen et al., 2011), Alzheimer disease, (Goutagny et al., 2013) and Parkinson's disease (de Hemptinne et al., 2013). The results of recent studies of Parkinson's patients during deep brain stimulation lead placement surgery demonstrate that the mechanisms of action of deep brain stimulation in movement disorders in general and Parkinson's disease specifically might be related to the modulation of PAC in motor cortex (de Hemptinne et al., 2015). In this study, we also wish to investigate the effects of direct cortical pulsed stimulation over motor cortex on the PAC signal and its correlation with the motor symptoms of the disease. This type of stimulation might provide a unique opportunity to investigate the mechanisms of action of cortical stimulation in Parkinson's disease and other movement disorders, along with possible therapeutic effects.

There is evidence that the basal ganglia may play some role in language. For example, recent studies of ischemic lesions and Parkinson's disease suggest that the basal ganglia play a role in the controlled processes supporting lexical-semantic processing (Copland et al. 2000a, b; Copland 2003). In that regard, speech irregularity such as soft speech (hypophonia) and reduced vocal loudness, monopitch, disruptions of voice quality, and abnormally fast rate of speech (hypokinetic dysarthria) are common speech related symptoms in Parkinson's disease and other movement disorders (Canter, 1963; Carter 1965; Ho et al. 1998). Such interruptions most commonly take place in the basal ganglia, where insufficiency of the level of dopamine causes slowed (bradykinesia) or failure to respond (akinesia) in speech production organs. The lips and tongue incompletely shape the appropriate formations for making the sounds of words; the vocal cords do not adjust for the quality of sound the words require; breathing may be inadequate to produce the volume of air necessary to produce adequate sound through the vocal cords (Coates et al. 1997; Pinto et al. 2004). Although deep brain stimulation of the subthalamic nucleus (STN) improves most of the motor symptoms in eligible PD patients but often does not result in consistent improvements in speech and in some cases may negatively impact language function (Lorinda et al. 2011). Here, we intend to use the unique opportunity of DBS lead placement surgery to provide access to the deep structures in the human brain and investigate the functional role of the basal ganglia in the speech production system.

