### **Timeline/Timing of Procedures Participants:**

All the testing procedures will be carried out in both intra- and extra-operative sessions; these procedures are described below in the section title '*Research Testing Procedures for both -- and Extra-operative Sessions*'. Healthy controls will be studied during extra-operative session, i.e. outside the operating room.

Patients who have chosen to have surgery may participate in up to three testing sessions. These testing sessions may include a session performed during the surgery; in the operating room (intra-operative session). Some patients will undergo one session prior to surgery, and/or another session after the surgery; these studies will be performed outside the operating room (extra-operative session).

Physiological monitoring of the central nervous system (CNS) will be carried out during both intra- or extra-operative sessions. CNS monitoring in the intraoperative sessions will include recordings of single neuron activity, local field potentials from microelectrode and surface electrodes, and the EEG. CNS monitoring in the extra-operative sessions will include EEG alone. Any intra- or extraoperative session may include monitoring through EKG electrodes, EMG electrodes, accelerometers, eye position sensors, and skin conductance monitors.

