#### **Objective I: Sensory Processes**

In these studies the patient is presented with a sensory stimulus (pain, visual, auditory, tactile) and the response is recorded. In most cases the sensory stimulus will be applied during a cognitive tasks engaging attention or learning. All experimental protocols and variables will be under computer control and will be carried out in healthy subjects or patients undergoing functional stereotactic procedures for movement disorders or pain.

Date: February 19, 2023

Principal Investigator: [name].

Application Number: NA\_00079932

The intra-operative studies will be carried out over multiple sessions; each session will include recordings from a single neuron. In many of these sessions, painful or nonpainful somatic stimuli, and other stimuli will be presented in a single train. The painful somatic stimulus will be a cutaneous laser stimulus (Themis, Starmed Tec, Starnberg, Germany) and the non-painful stimulus will be a cutaneous electrical stimulus (DS7A, Digitimer, Hertfordshire, UK). The length of the sessions will be less than one hour and twenty minutes in total.

Analysis of the response to these stimuli will include source modeling, and is carried out to estimate the location of the cortical generator for the evoked potential, and activation resulting from that stimulus. Subsequent studies will examine sites activated in a coherent fashion during the processing of the sensory stimulus. Analysis of single neuron and LFP recordings will look for evidence of desynchronization, coherence and directed functional connectivity between different structures. The results will be interpreted as evidence of connectivity within sensory networks. All experimental protocols and variables will be under computer control.

During the testing sessions, we will also measure the salivary cortisol levels. Cortisol levels are responsive to acute stress and acute tonic pain (Zimmer et al., 2003; Dedovic et al., 2009). Subjects will be informed to not engage in moderate exercise or consume food or drink two hours before the testing sessions (Hansen et al., 2008).

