### ***Objective I:***

Under Objective I we will determine functional connectivity between structures at which single neuron and LFP responses occur in response to painful laser stimuli. Secondary outcome variables will address cognitive processes related to sensory stimuli and the networks which subserve them. These networks will be defined by measures of functional connectivity between electrode sites such as correlation, coherence, and causal (directed) interactions.

Network characteristics will be estimated by measures of connectivity at the time of laser stimuli between sites such as correlation, coherence, functional connectivity, and causal interactions.

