#### Implanted EEG electrodes:

Subdural strip electrodes consist of a series of metallic electrodes mounted in thin plastic in such a way that it can lie smoothly on the surface of the cortex. They provide high amplitude ECoG signals, and are widely used for monitoring, seizure mapping and stimulation for functional mapping. Subdural strip electrode implantation, mostly used for identifying the epileptogenic focus in epilepsy patients, is a relatively safe procedure (Wyler et al., 1984). The application of strip electrodes is not restricted to epilepsy patients. In movement disorder patients, positive effects of chronic motor cortex stimulation via epidurally implanted electrodes have been first reported by Canavero and Paolotti (2000) and Canavero et al., 2002 and Canavero et al., 2003, by implanting the strip electrodes extradurally over M1 via a small craniotomy. The results of recent studies on Parkinson's patient during deep brain stimulation surgery demonstrate that subdural strip electrode implantation over human motor cortex is safe (de Hemptinne et al., 2013, de Hemptinne et al., 2015). These recordings provide a unique opportunity to investigate the mechanisms of action of deep brain stimulation in

Date: February 19, 2023

Principal Investigator: [name].

Application Number: NA\_00079932

movement disorders in general and Parkinson's Disease specifically (Crowell et al., 2012, de Hemptinne et al., 2013, de Hemptinne et al., 2015).

In traditional subdural electrode strip placement procedures, the associated risk of infection is greatest when there are more than 100 electrode contacts implanted, an excess of 10 exiting electrode cables, or if the electrodes remain for 14 days or more (Fountas , 2011). Infection is not a major risk in the procedure as proposed because the electrode is left in place for a much shorter time span (4 hours) than typical strip placement procedures (7-14 days). Additionally, the cables pertaining to the electrodes remain within the sterile field for the duration of the procedure, further decreasing the risk of infection. Another risk of electrode placement is hemorrhage. Significant intracerebral hemorrhage has been reported, with an incidence of 2.5% from 1,582 patients assessed with depth electrodes from a literature review (Pilcher et al., 1993, 2004), and 1% or less incidence in a more recent study (Blume, 1997).

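### Measurement noise on the driving signal can make a one-way link look two-way in the Granger-type measure, which the plan reads as causal with no noise check

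*Combined protocol and SAP*

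**What the plan says.** Section 3 (Background), citing the Granger reference among others, defines the directed measure: "causality is a measure of the extent to which signals at one electrode are causal of those at another electrode". The same paragraph says what it is for: "Cortical or deep structures jointly processing sensory signals will be identified by calculation of correlation, coherence and causality between the EEGs or LFPs recorded".

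Section 4 (Objective I: Sensory Processes) carries this into the analysis: "Analysis of single neuron and LFP recordings will look for evidence of desynchronization, coherence and directed functional connectivity between different structures". It adds that the results will be taken as evidence of connectivity in sensory networks. Section 7 (Objective I) makes the measure part of an outcome: "These networks will be defined by measures of functional connectivity between electrode sites such as correlation, coherence, and causal (directed) interactions".

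Section 4 (Timeline/Timing of Procedures) lists the intra-operative signals as "recordings of single neuron activity, local field potentials from microelectrode and surface electrodes, and the EEG". For the other setting it says "CNS monitoring in the extra-operative sessions will include EEG alone". The only remark on relative signal quality concerns subdural strips, in Section 8: "They provide high amplitude ECoG signals".

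No section gives a noise level, model order, epoch length, sampling rate, significance rule, surrogate or time-reversed control for the directed measure, or any caveat on its causal reading. Section 7 describes the study as exploratory, with mainly descriptive and graphical summaries.

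**The concern.** The sentence in Section 3 and the quantity that a Granger-type index estimates are different things. The sentence is about one site's signal causing another's. The index is about whether the past of recorded Y adds to the past of recorded X in predicting recorded X. The two separate when the driving signal is recorded with noise: the driven site then holds extra information about the driver's own past, and the index becomes non-zero in a direction in which no connection exists.

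Directed interactions help to define the Objective I networks, and some of the background reasoning is directional. For example, Section 3 (Objective II: Motor Control) offers a pallidum-to-thalamus-to-cortex explanation of dystonia. A one-way pathway that appears in the results as two-way would misdescribe the network. Because the index itself is biased, a purely descriptive summary inherits the error.

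**Working it through.** The documents state no figure for this point, so there is none to reproduce. The check is a short argument followed by simulation on assumed inputs.

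**Step 1: when the reverse index is non-zero.** Let X drive Y one way, with X autocorrelated (as a rhythm is) and containing no Y term:

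- Y_t = 0.5·Y_{t−1} + c·X_{t−1} + e_t
- recorded signals: x_t = X_t + m_t and y_t = Y_t + k_t, with independent white noises m and k
- noise-to-signal variance ratios: rx = var(m)/var(X), ry = var(k)/var(Y)
- reverse index: F(y→x) = ln[ var(x_t | past x) / var(x_t | past x and past y) ]

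Three cases follow, given a model order long enough for X's own dynamics:

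- rx = 0: past x is the past of X itself, so past y adds nothing and F = 0, whatever ry is.
- rx > 0 and c ≠ 0: past x is a blurred record of X. Because y_{t−1} contains c·X_{t−2}, past y supplies a second reading of X, so F > 0 although Y does not drive X.
- c = 0: y carries nothing about X, so F = 0 whatever the noise.

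The conditions are therefore a real forward link and noise on the driver. Noise on the target only makes the second reading poorer.

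**Step 2: size.** All inputs are assumptions: X a 20 Hz AR(2) oscillator sampled at 200 Hz, or an AR(1) with coefficient 0.9; bivariate Granger F test at 5%; 500 replicates. The Monte Carlo standard error at 5% is √(0.05 × 0.95/500) ≈ 1 percentage point. The table gives the percentage of runs rejecting in the absent direction Y→X, by rx/ry.

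| Setting | 0/0 | 0/1 | 0.1/0 | 1/0 | 0.1/0.1 | 1/1 |
|---|---|---|---|---|---|---|
| Oscillator, c=0.3, order 5, n=2000 | 3.8 | 4.0 | 77.8 | 100 | 70.0 | 100 |
| Oscillator, c=0.3, order 5, n=500 | 5.4 | 5.4 | 24.2 | 97.8 | 16.4 | 69.8 |
| Oscillator, c=0.1, order 5, n=2000 | 4.0 | 4.2 | 13.4 | 94.0 | 12.8 | 68.0 |
| Oscillator, c=0.1, order 10, n=500 | 3.6 | 5.6 | 5.4 | 19.8 | 5.6 | 11.6 |
| AR(1), c=0.3, BIC order, n=2000 | 7.0 | 3.8 | 25.6 | 100 | 22.6 | 97.0 |

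The true direction X→Y was rejected in 93% to 100% of oscillator runs, so most inflated cases would look two-way. With no coupling, noise on one or both sites left both directions at 3.4% to 6.2%.

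**Step 3: a second layout.** 20 Hz rhythm, 250 Hz sampling, one-second epochs, order 8, drive at a lag of 3 samples, 300 runs per cell. Driver noise SD was 0, 0.5, 1 and 2 relative to X, that is, signal-to-noise 1/SD²: none, 4, 1 and 0.25. False reverse rejection was 4%, 69%, 100% and 100% with 20 epochs, and 6%, 96%, 100% and 100% with 40. A 20-epoch, order-8 run at coupling 0.3 (60 runs per cell) gave 2% with no noise or target-only noise, and 100% with driver noise, equal or unequal. At coupling 0.05 the range was 7% to 100%.

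**Step 4: does a net-direction check help?** In the AR(1) system the sign of F(x→y) − F(y→x) gave the true direction in 84% to 100% of runs, and a time-reversal contrast gave the same range. In the second layout the time-reversed rule was right in 86% to 100% of runs and wrong in none. At coupling 0.05, however, it kept only 32% to 85% of the one-way links that the forward test found in 100% of runs. Truly reciprocal systems were labelled one-way in 98% to 100%. Used as a bare sign rule without surrogates, it picked a direction in 70% to 95% of uncoupled runs.

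**The case against.** The strongest reply is that the plan is exploratory and descriptive. It speaks of a measure of extent and states no null hypothesis, alpha or rejection rule. It nowhere says that two non-zero directions will be called a reciprocal loop. The estimator and its controls may lie in the cited works, which are not available here. The directed measure is one of several, and the Abstract also plans electrical stimulation as further evidence of the networks. All of this stands, and it limits the point. It does not remove it: the causal reading is in the plan's own words, the index is biased whether or not it is tested, and no caveat or check is given.

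A reader might infer more than the documents support:

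- *That unequal noise between deep, strip and scalp signals is the cause.* It is not. Equal noise gave 70.0% and 100% in the first row of the table, while a clean driver with a noisy target gave 4.0%. The documents also give no noise level for any signal type.
- *That noise invents connections from nothing.* A real link in one direction is needed.
- *That direction is the content of both hypotheses.* As stated in the Abstract, the first concerns involvement in pain signaling and the second concerns distorted signals between structures. Neither fixes a direction.
- *That the simulated rates are this study's error rates.* Every input to them is assumed.

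**Conclusion.** The concern holds in this form: the plan reads a Granger-type measure as one signal causing another, and noise on the driving signal can make a genuine one-way link appear two-way. It applies to intra-operative recordings and equally to EEG-only sessions, since mixed recording types are not required.

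The direction of the error is clear, but its size in this study is not known. Under the assumed settings, false reverse rejection ran from about 5% (weak coupling, high model order, short record, little noise) to 100% (stronger coupling or more driver noise with longer records). The result rests on additive white noise and two channels; shared reference and field spread were not simulated. This is an interpretive weakness that should be corrected before directed results are reported. It does not invalidate the recordings or the other connectivity measures.

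**What to change.** Make three changes of wording and one added analysis:

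1. In Section 3, replace *are causal of* with *improve prediction of*.
2. In Section 7, state that non-zero results in both directions will not by themselves be reported as a reciprocal pathway.
3. In Section 7, state that each directed result will be accompanied by a sensitivity analysis giving the net difference between directions and its value in time-reversed data, with significance from epoch surrogates.
4. Report this beside the forward estimates, not as a condition for reporting them.

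No new recordings are needed; the same estimator is re-run on existing data. The cost is a little more analysis and more cautious directional claims. The check should not become a mandatory gate: as such it would miss weak one-way links and reduce truly reciprocal links to a net direction. It lessens the problem but does not guarantee the right direction.
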